### **Blood sample collection and processing:**

Blood will be collected in the morning during the routine blood draw on the wards. Samples for plasma and RBC fatty acids will be collected in EDTA containing tubes, and

samples for pre-albumin and hs-CRP in tubes without anticoagulant. The tubes will be centrifuged ( $910 \times g$ , 10 min), and serum and plasma will be aliquoted and stored at  $-80^{\circ}C$  until analysis.

From the plasma tube, all remaining plasma and the buffy coat, which shows on top of the erythrocyte sediment as a white ring will be discarded. The remaining packed RBC will be aliquoted and frozen at  $-80^{\circ}C$  until analysis.

Pre-albumin and hs-CRP will be measured by routine methods at an accredited laboratory (Hospitals In-Common Laboratory Inc., Toronto).

Red blood cell and plasma fatty acid profile will be assessed using gas chromatography. Briefly, total lipids will be extracted from RBC or plasma into chloroform/methanol (47), containing butylated hydroxytoluene as antioxidant. Extracted lipids will be saponified and transmethylated using boron-triflouride (48). Fatty acid methyl esters were then separated using an Agilent 6890 gas chromatograph equipped with a flame ionization detector (49). Peaks will be identified from C14:0 to C22:6n-3. The relative amount of the essential fatty acids, alpha-linoleic acid and linolenic acid will be reported as % of total lipids.

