Measurements: :**Part A** 1) Patient demography: age, sex; 2) Type of patient: medical, surgical and/or ICU patients; 3) Type of any surgery the patient has during hospitalization; 4) Primary indications related to parenteral nutrition, comorbidities, updated CCI (31,32); 5) Nutritional assessment: weight, height, BMI, SGA, estimated energy and protein requirements; 6) comparison of energy received as a goal vs calculated energy requirements using published equations; 7) Energy, dextrose, aminoacids and lipids received by PN.

Total energy and proteins received including enteral nutrition and oral intake. Energy provided by Propofol, if received. In case of enteral nutrition, name and amount of product used; 8) Type of line used (peripheral or central); 9) Vascular access; 10) Reason for ending PN; 11) Number of times and reasons for interruption of PN; 12) Weekly PN related laboratory results; 13) Complications secondary to PN; 14) Outcome of patient

**Part B:** We will include the same measurements as in part A, but will add some additional nutritional parameters which will be done at baseline (Day 0) and after 10 days (Day 10)

with PN. Baseline or day 0 assessments to be done prior to or within 24 hours of PN initiation. Day 10 measurements to be done on day 10 of PN administration. If the PN ends before day 10, we will consider a cutoff at day 7 of PN. This means that if the PN ends before day 7, we will not repeat the measurements or blood work. If PN ends between days 7-9 we will repeat the measurements instead of doing them on day 10 for this special cases.

The parameters to measure will be: hand grip strength (kg), mid arm circumference (cm), SGA and weight as measures of nutritional status. We will also add hs-CRP, pre-albumin, and fatty acid profile in red blood cells (RBC) and plasma to the laboratory results at both time points. Clinical outcomes (documented infections, antibiotic-days or other adverse events) will be monitored for one week post-PN. In addition, mortality and length of stay will be documented for the entire hospitalization.

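### No wash is specified for the packed red cells before freezing, so trapped plasma can bias the RBC fatty acid comparison between lipid groups, by an amount the documents cannot settle

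*Combined protocol and SAP*

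**What the plan says.** The section Blood sample collection and processing gives the sequence from tube to freezer. Tubes are spun once (910 × g, 10 min) and plasma is aliquoted. Then "all remaining plasma and the buffy coat, which shows on top of the erythrocyte sediment as a white ring will be discarded". The RBC step ends: "The remaining packed RBC will be aliquoted and frozen at" −80 °C. No wash, second spin or correction for trapped plasma appears there or elsewhere. For the assay, "total lipids will be extracted from RBC or plasma into chloroform/methanol", and the essential fatty acids "will be reported as % of total lipids".

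On timing, the same section says: "Blood will be collected in the morning during the routine blood draw on the wards". Study design adds, for Part B: "Day 10 measurements to be done on day 10 of PN administration". Patients whose PN ends on days 7–9 are measured then, and those whose PN ends before day 7 have no repeat sample. Day 0 assessments may be made before PN starts or in its first 24 hours. No interval between lipid infusion and blood draw is stated. Part B adds the "fatty acid profile in red blood cells (RBC) and plasma to the laboratory results at both time points".

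Part B lists essential fatty acid status as a secondary outcome. Under Statistical analysis, changes in laboratory results are compared between groups. The Background describes Intralipid as soybean oil rich in omega-6 polyunsaturated fatty acids, and ClinOleic as 80% olive oil and 20% soybean oil.

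**The concern.** Taking plasma off the top of a spun tube does not remove the plasma lying between the packed cells. The extraction takes total lipid from the whole aliquot, and no membrane isolation or lipid-class separation is described, so lipid from that plasma is counted as RBC lipid. The result is a relative percentage, so the carry-over shifts it directly.

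If the carry-over were the same in both groups it would matter little. Here its composition can follow the assigned emulsion, because the follow-up sample is taken on PN and the emulsions differ by design. Lipid need not be infusing at the moment of the draw: any difference in plasma fatty acids between the groups at day 10 is enough. The resulting error is systematic, so neither more patients nor the covariate adjustment in Statistical analysis removes it. At stake is how a group difference in RBC fatty acids is read, since part of it could be plasma lipid rather than a change in the cells.

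**Working it through.** The plan states no figure for trapped plasma or for RBC fatty acids, so there is nothing of its own to reproduce. The check is a two-component mixing model.

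**1. Plasma share of the aliquot's fatty acids.** Let f be trapped plasma as a fraction of packed-cell volume, and r the plasma fatty acid concentration divided by that of the cells. Then

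w = f·r / (f·r + 1 − f).

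Both inputs are assumptions: f = 2–10%, r = 1–3.

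| f | r = 1 | r = 2 | r = 3 |
|---|---|---|---|
| 2% | 2.0% | 3.9% | 5.8% |
| 5% | 5.0% | 9.5% | 13.6% |
| 10% | 10.0% | 18.2% | 25.0% |

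The two corners are 0.02/(0.02 + 0.98) = 0.020 and 0.30/(0.30 + 0.90) = 0.250.

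**2. Error in the group comparison.** Take w as equal in both groups, and let P and R be the between-group differences in plasma and in the cells themselves, in percentage points of one fatty acid.

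Observed RBC difference = (1 − w)·R + w·P

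Error = observed − R = w·(P − R)

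**3. Size when the cells do not differ (R = 0).** With P assumed to be 5–15 points:

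- lowest: 0.020 × 5 = 0.1 point
- f = 5%, r = 1, P = 10: 0.050 × 10 = 0.5 point
- f = 5%, r = 2, P = 10: 0.095 × 10 = 0.95 point
- highest: 0.250 × 15 = 3.75 points

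**4. Size when the cells do differ.** If R moves in the same direction as P, the error shrinks. With w = 0.095, P = 10 and R = 5, it is 0.095 × (10 − 5) = 0.48 point, half the value at R = 0.

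**5. Change from baseline.** Before PN starts there is no emulsion-related plasma difference, so subtracting a pre-PN sample removes none of the day 10 carry-over that depends on the emulsion. A day 0 sample taken during the first 24 hours of PN may already contain the assigned emulsion, and subtracting it removes some. Overall the removal is partial.

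**6. Whether such a shift could reach significance.** This needs a further assumption, an SD of 1.5–2.5 points for the RBC measure. With R = 0, a two-sided normal test at 0.05 and SE = SD·√(2/n):

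| Shift | n per group | Probability of p < 0.05 |
|---|---|---|
| 0.1 point | 150 | 6–9% |
| 0.5 point | 150 | 41–82% |
| 0.5 point | 100 | 29–65% |
| 0.5 point | 50 | 17–39% |

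The planned 150 per group is an upper limit here, because patients with less than 7 days of PN give no second sample. With complete washing f and w are about 0, the error is about 0 and the rate returns to 5%.

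**The case against.** The strongest reply is that nothing here is demonstrated. The plan is silent on washing, which is not a statement that cells go unwashed. The assay is described only in outline and rests on cited methods that cannot be consulted. Every input to the size is assumed, the results span about 37-fold (3.75/0.1), and the documents give no SD or relevance threshold to judge them against. Plasma is measured on the same occasions, so the plan has some means of examining the problem. A wash also costs centrifuge time on a large number of samples.

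Much of this stands. A reader might infer that the cells are known to be frozen unwashed. The documents support only that no wash is specified, although the preparation is detailed enough to describe the look of the buffy coat, and the abridged account begins only after the freezing step. A reader might also infer that the plan cannot separate plasma carry-over from change in the cells. That is too strong, because the paired plasma profile allows an approximate correction. Nor do the documents name RBC as the readout of membrane incorporation: they list essential fatty acid status and measure both matrices. Whether lipid is infusing at the morning draw is likewise not stated.

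What the reply does not remove is the mechanism. Followed as written, the procedure leaves some plasma in an aliquot reported as RBC, and the composition of that plasma can differ by group.

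**Conclusion.** The point holds as a low-priority improvement. As written, the preparation can bias the between-group RBC comparison by w × (plasma difference − true RBC difference). With no true RBC difference and the assumed ranges (f 2–10%, r 1–3, plasma difference 5–15 points), that is about 0.1 to 3.75 percentage points, negligible at the low end and possibly material above it. The documents cannot place the trial within that range, so they do not support a conclusion that an RBC difference would be an artefact, or that the bias is material. Length of stay, infections, mortality, hs-CRP, pre-albumin and the plasma profile are unaffected.

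**What to change.** In Blood sample collection and processing, add a saline wash and re-spin of the packed cells after plasma and buffy coat are removed and before aliquoting and freezing, at both day 0 and day 10. If the laboratory already does this, one sentence saying so settles the point. The step must come before freezing, because intact cells cannot be washed after a thaw. Also record the draw time relative to lipid infusion at both time points.

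Flag any samples already frozen unwashed. For these, report the RBC profile as exploratory, with a sensitivity analysis over a stated range of w:

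corrected RBC % = (observed RBC % − w × paired plasma %) / (1 − w).

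The plan reports relative percentages only. Recording total fatty acid concentrations in plasma and RBC would inform r, leaving f as the main assumption.

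The cost is saline, bench time and centrifuge time. At the plan's own 10-minute spin, one wash adds 10 minutes per batch and two add 20, over at most 600 samples (300 patients × 2). No extra blood or visit is needed. If some samples are already stored unwashed, the trial will hold two sample types, which should be analysed separately.

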Intralipid is a soybean oil (SO) intravenous fat emulsion, available since 1961, rich in omega-6 polyunsaturated fatty acids (PUFA) and may enhance the generation of arachidonic acid-derived eicosanoids that could exaggerate the inflammatory response during stress and trauma (26). This pro-inflammatory effect may be detrimental. For example, in a prospective, randomized, controlled study comparing the vascular, metabolic, immune and inflammatory effects of 24h- infusion of parenteral nutrition (PN) with SO-based lipid emulsion (Intralipid), olive oil-based lipid emulsion (ClinOleic), lipid free and normal saline in 12 healthy subjects, the authors found that Intralipid increased blood pressure and altered endothelial function (27). A recent ASPEN position paper (28) reviewed the literature on lipid emulsions. While the current available, standard SO-based lipid emulsion like Intralipids meet the needs of most PN patients, alternative oil-based fat emulsions, like olive oil (OO) are used extensively in Europe and have been shown to be less proinflammatory and immunosuppressive due to different metabolic pathways. Patients receiving these alternative lipid emulsions may have better clinical outcomes but further research is needed to identify which type of lipid emulsion or which combination of oils may be most clinically useful for specific patient populations. SO lipid emulsions have plant sterols known as phytosterols, these are thought to alter hepatic function and have been associated with cholestasis in children on long-term PN (29,30). Also, most SO lipid emulsions have small amounts of  $\alpha$ -tocopherol, a known antioxidant. Studies have shown that vitamin E has a role in the prevention of hepatic injury in animal models(31), but there is still deficit in human data.

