ClinOleic is a lipid emulsion composed of OO (80%) and SO (20%) (27,32). It is a third-generation of lipids and was introduced in Europe in the 1990s (28) . It has more monounsaturated fatty acids (MUFA) than PUFA, in a proportion of 65% MUFA and 20% PUFA (32). Even though it has a lower proportion of PUFA, no significant changes in plasma fatty acid profile and no deficiency of essential fatty acids have been reported (33). However, this was observed in a mouse model (34). ClinOleic is also rich in  $\alpha$ -tocopherol, and MUFA are resistant to lipid peroxidation so this intravenous lipid emulsion is potentially beneficial in subjects with risk of oxidative stress (32). There is a lack of studies that critically evaluate indications and outcomes regarding parenteral nutrition in different hospital units and in a wider variety of pathologies. There are very few studies published that compare two types of intravenous lipid emulsions and all have limited number of patients. There is a need to elucidate if the new lipid generations are a better option than the classic SO-based lipid emulsions and which patient populations will benefit most from them. This and our personal need for evaluating the indications and outcomes of patients with parenteral nutrition motivated us to do this study in our own center.

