## **Part B: Intralipid vs ClinOleic**

### **Primary Objective**

To evaluate metabolic, nutritional, infectious and inflammatory parameters in patients receiving SO-based lipid emulsion compared to those of patients receiving OO -based lipid emulsion.

- Primary Outcome: length of stay
- Secondary Outcomes: mortality, nutritional parameters (anthropometry, handgrip-strength, mid-arm circumference, , pre-albumin), inflammation (high sensitivity C-reactive protein; hs-CRP), documented infections, ICU stay, antibiotic-days, liver enzymes, essential fatty acid status

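### Essential fatty acid status in Part B is read only from the relative percentages of two parent acids, which cannot separate the composition of the infused emulsion from impaired status

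*Combined protocol and SAP*

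**What the plan says.** The secondary outcomes under Part B: Intralipid vs ClinOleic include "liver enzymes, essential fatty acid status". No definition, threshold or direction of harm is attached.

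The Part B measurements in Study design add "fatty acid profile in red blood cells (RBC) and plasma to the laboratory results at both time points". These time points are day 0 (before, or within 24 hours of, the start of PN) and day 10. If PN stops on days 7 to 9 the second sample is taken then; if it stops before day 7 there is none.

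Blood sample collection and processing has blood taken at the routine morning draw, lipids extracted from red cells or plasma, and methyl esters separated by gas chromatography. "Peaks will be identified from C14:0 to C22:6n-3". The only reporting rule follows: "The relative amount of the essential fatty acids, alpha-linoleic acid and linolenic acid will be reported as % of total lipids".

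On the emulsions, the Background gives ClinOleic's fat "in a proportion of 65% MUFA and 20% PUFA" and describes Intralipid as rich in omega-6 polyunsaturates, without a percentage. Study design makes the lipid calories equivalent. Statistical analysis does not name fatty acids. They fall under other laboratory results, whose changes are compared between arms at two-sided alpha 0.05.

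**The concern.** The readout is a relative amount of acids that the two infusions supply in different quantities. If linoleic acid is a smaller share of the sample on ClinOleic, there are two explanations: the sample contains or reflects an oil with less of it, or the patient's essential fatty acid status has suffered. The plan reports nothing that distinguishes these and gives no rule for reading a difference.

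This matters because the Background itself raises the question for ClinOleic. It says that, despite the lower polyunsaturated share, "no deficiency of essential fatty acids have been reported", and then mentions a contrary observation in mice. A trial meant to add to that evidence needs a measure that bears on status and not only on supply. Equally, if status did deteriorate, no prespecified quantity would show it.

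Two wording faults compound the problem. A methyl-ester chromatogram gives shares of total fatty acids; total lipid is never quantified in the described method, so the stated denominator does not match. The acid names are also crossed: the essential pair is linoleic and alpha-linolenic. Finally, arachidonic acid is not among the reported acids, although the Background's mechanism for Intralipid is that it "may enhance the generation of arachidonic acid-derived eicosanoids".

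**Working it through.** The documents state no effect size, SD or power for this outcome, so there is no plan figure to reproduce. The steps below illustrate the possible size in plasma.

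**Inputs from the documents.** ClinOleic 20% polyunsaturated and 65% monounsaturated (Background); equal lipid calories (Study design); 150 per arm (Feasibility and Sample Size); two-sided alpha 0.05 (Statistical analysis).

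**Assumptions, not in the documents.** Intralipid polyunsaturated share 40% to 65%; linoleic share of the bag 18% for ClinOleic and 52% for Intralipid; habitual plasma linoleic acid 30% of fatty acids; infused oil 10% to 30% of plasma fatty acids at the draw; SD of change 4 to 6 points; 75 per arm as a low case for patients with a repeat sample.

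**Step 1: supply.** At equal lipid calories, ClinOleic delivers 20/65 = 0.31 to 20/40 = 0.50 of the polyunsaturated fat that Intralipid delivers.

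**Step 2: mixing.** If a share w of plasma fatty acids is infused oil, linoleic % = (1 − w) × 30 + w × bag linoleic %.

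| w | ClinOleic | Intralipid | Gap (points) |
|---|---|---|---|
| 0.10 | 28.8 | 32.2 | 3.4 |
| 0.20 | 27.6 | 34.4 | 6.8 |
| 0.30 | 26.4 | 36.6 | 10.2 |

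The baseline cancels: the gap is w × (52 − 18). As a sensitivity check on total polyunsaturates, w × (S − 20) with Intralipid share S from 40 to 65 gives 2.0 to 4.5 points at w = 0.10 and 6.0 to 13.5 at w = 0.30.

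**Step 3: fall within the ClinOleic arm.** If infused ClinOleic enlarges the pool by a fraction x, linoleic % = (30 + 18x)/(1 + x). For x = 0.1, 0.2, 0.3 this is 28.9, 28.0 and 27.2, a fall of 1.1 to 2.8 points. Treating the added oil as free of linoleic acid, 30/(1 + x), would give 27.3 to 23.1, a fall of 2.7 to 6.9. That overstates the effect, because ClinOleic contains soybean oil.

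**Step 4: detectability.** The difference detectable with 80% power is (1.960 + 0.842) × SD × √(2/n).

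| SD of change | n = 150 per arm | n = 75 per arm |
|---|---|---|
| 4 | 1.29 | 1.83 |
| 6 | 1.94 | 2.74 |

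The gaps in step 2 for linoleic acid exceed all four values. Smaller compositional differences might not be detected: for 0.95 points (a 20% baseline diluted by 5%, 20 − 20/1.05), power is only 0.16 to 0.54 over the same four cases.

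**Step 5: are other indices available?** Both 20:3n-9 and 20:4n-6 are 20-carbon acids within the C14:0 to C22:6n-3 range already identified, so their ratio needs no new sample.

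None of this arithmetic applies to red cells. Plasma and buffy coat are discarded before the cells are frozen, and the documents give no basis for a figure there.

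**The case against.** The strongest reply has four parts.

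First, a reader might infer that the trial will report worse essential fatty acid status on ClinOleic when none exists. The documents do not support that. They set a reporting format and nowhere say that a lower percentage means worse status. A smaller linoleic supply at equal calories is also a real difference in provision, not a measurement artefact. This stands. The fault is that the plan is silent on interpretation, leaving it to be settled after the data are seen.

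Second, a reader might infer that a between-arm difference is all but guaranteed. The Background sentence that reports no deficiency also reports no significant change in the plasma profile on ClinOleic. Its source cannot be seen here and may not be a comparison with Intralipid, so it does not settle the matter, but it rules out certainty.

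Third, the profile is measured in red cells as well as plasma and is wider than two acids, so other indices could be derived later. That is correct, and it makes the remedy cheap. An index chosen after the results are known is weaker than one fixed beforehand.

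Fourth, the 20:3n-9/20:4n-6 ratio comes from general fatty acid biochemistry and is not mentioned in the documents. That is also correct. The need for a prespecified measure follows from the documents; this particular ratio is a proposal.

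**Conclusion.** The point holds in a limited form. Essential fatty acid status has no operational definition, and the one stated readout cannot separate emulsion composition from impaired status. That conclusion rests on the documents alone: the reporting sentence, the compositional difference and the equal lipid calories.

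The size does not. Under the stated assumptions a purely compositional plasma gap of 3.4 to 10.2 points is possible and would usually be detectable. With less infused oil in the sample or a larger SD it could go unnoticed. The ambiguity is greatest for plasma, because the second sample is normally taken during PN, no pause in lipid infusion is described, and the baseline draw may follow the start of PN by up to 24 hours. It is not quantified for red cells.

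One secondary outcome is affected. Length of stay as the primary outcome and the planned 150 per arm are not. The mismatched denominator and the crossed acid names are plain wording errors that should be corrected in any case.

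**What to change.** Amend Blood sample collection and processing as follows.

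- From the same chromatograms, at day 0 and at day 10 (or days 7 to 9), compute the 20:3n-9/20:4n-6 ratio in plasma and in red cells. Name it as the between-arm measure of essential fatty acid status, with a rise read as the unfavourable direction.
- Report linoleic, alpha-linolenic, oleic and arachidonic acid as percentages of total fatty acids. State in advance that the linoleic, alpha-linolenic and oleic percentages describe lipid exposure.
- Correct the acid names to linoleic and alpha-linolenic, and replace total lipids as the denominator.
- Name the ratio in Statistical analysis among the outcomes compared by change.

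The cost is protocol wording and the integration of peaks within the range already identified, with no extra blood, visits or staff. The drawback is that 20:3n-9 is a small peak, so some values may lie near the detection limit. The plan should say how such values will be handled.
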